**Appendix C - Hospital Survey**

Questions	Options
How many beds does your hospital have?	
How many ICU beds does your hospital have?	
Does your hospital have a high dependency unit (HDU)?	Yes/no
(If yes) how many beds does your HDU have	value
Do you have an interventional radiology service at your hospital?	Yes/no
Do you have an endoscopy service at your hospital?	Yes/no
Is ERCP routinely offered to patients in your hospital?	Yes/no
Is EUS routinely offered to patients in your hospital?	Yes/no

**Appendix E - Charlson Comorbidity Index**

Comorbidity	Scoring
Age	0 points (<50 years) 1 point (50 - 59 years) 2 points (60 - 69 years) 3 points (70 - 79 years) 4 points (≥ 80 years)
Previous myocardial infarction (MI)	1 point
Congestive heart failure (CHF)	1 point
Peripheral vascular disease	1 point
Previous cerebrovascular accident (CVA) or transient ischaemic attack (TIA)	1 point
Dementia	1 point
COPD	1 point
Connective tissue disease	1 point
Peptic ulcer disease	1 point
Liver disease	1 point (mild) 3 points (moderate to severe)
Diabetes mellitus	0 point (none or diet-controlled) 1 point (uncomplicated) 2 points (end-organ damage)
Hemiplegia	2 points
Moderate to severe chronic kidney disease ( Moderate = creatinine > 3mg/dL (0.27 mmol/L), Severe = on dialysis, status post kidney transplant, uraemia )	2 points
Solid tumour	0 point (none) 3 points (localised) 6 points (metastatic)
Leukaemia	2 points
Lymphoma	2 points
Acquired immunodeficiency syndrome (AIDS)	6 points
Total Charlson Comorbidity Index (maximum score = 37)	

**Appendix F - Tokyo guidelines diagnostic criteria for cholangitis**

Class	Criteria
A. Systemic inflammation	
 
1. Pyrexia (>38 degrees Celsius)
 
2. White blood cells <4 or >10 ×1,000/μL and/or CRP ≥1
 

B. Cholestasis	
 
1. Jaundice: T-Bil ≥2 (mg/dL)
 
2. Deranged liver function tests (>1.5 × STD)
 

C. Imaging	
 
1. Biliary dilation
 
2. Evidence of aetiology on imaging
 

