# 1. Background and rationale

Acute pancreatitis (AP) is one of the most common gastrointestinal conditions resulting in hospital admission. It has an estimated annual incidence of 58 per 100,000 in Aotearoa-New Zealand (AoNZ) adults (1–3). AP is characterised by a local and systemic inflammatory response with variable clinical progression, from mild to severe as defined by the degree of organ dysfunction (4). The majority of patients with AP suffer only mild disease that is self-resolving. However, 20% develop moderate or severe AP, which involves pancreatic or peripancreatic necrosis, organ failure, or both. Severe pancreatitis is a serious condition with a risk of mortality between 20-40% (5–8). Despite substantial disease burden, there are no effective therapies that alter the course of disease and management remains largely supportive.

In the last decade, a number of landmark clinical trials have provided substantial guidance on the management of the AP, particularly with regards to antibiotic use, endoscopic retrograde cholangiopancreatography (ERCP)(9), and management of necrosis (10,11). Furthermore, multiple scientific bodies have developed and disseminated evidence-based guidelines for managing AP. However, their adoption into clinical practice remains suboptimal. An international cohort study that assessed the compliance rate with current guidelines in the treatment of patients with acute biliary pancreatitis showed a wide variability of practice (12). While it is commonly believed that noncompliance with published guidelines indicates areas in which recommendations are based on insufficient evidence, previous studies have shown a lack of compliance even in areas where randomised controlled trials (RCTs) have already resolved controversial issues during the last 10 years (12,13).

A multicentre national observational study will enable the assessment of compliance to quality performance indicators (QPIs) for the early management of AP in the AoNZ context. Furthermore, it will demonstrate any potential excess morbidity associated with noncompliance to best evidence driven clinical practice. Currently there is no such data for AoNZ. This data can be used to standardise and optimise care nationally to create more equitable outcomes for all patients.

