8	Fluids	
 
All patients commenced on IV Hartmann's solution within one hour of admission to the emergency department by a clinician and at an initial rate of 5-10 ml /kg in response to hypovolemia until resuscitation goals reached.
 
Then a rate of 1-2 ml/kg/hour for patients not tolerating PO in the first 48 hours.
 
	IAP	IV fluids N / Y Time commenced from admission What initial fluid was given? Initial prescribed rate Initial received rate Average rate 2 nd 24 hours Average rate 3 rd 24 hours Fluid bolus given (# times and and timing) Volume / 24 hours over 72 hours?
9	Anticoagulation	All patients with predicted severe AP considered for or started on anticoagulation within 24 hours of admission	-	Anticoagulation N / Y Medication prescribed When started (hours from admission)
10	Antibiotics	Antibiotic prophylaxis not recommended for the prevention of infectious complications in AP	IAP	Antibiotic N / Y Antibiotic indication

11	Nutrition	
 
1. No patients made 'nil-by-mouth' and no food withheld unless there was a clear reason.
 
2. Offer EN to anyone with MSAP or SAP starting within 72 hrs.
 
3. PN avoided unless EN fails or is contraindicated
 
	NICE	Initial NBM N / Y From admission given trial of light diet. N / Y Initial NG or NJ? EN started within 72 hours if needed N / Y EN prescribed rate PN started if EN was not tolerated or contraindicated.
12	ERCP/ES	ERCP is indicated in patients with biliary pancreatitis and acute cholangitis within 48 hours of admission.	IAP	ERCP N / Y Indication: cholangitis or cholestasis When done? (hours)

\* Reference of guideline from which the QPI is primarily taken from

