Type of opioid prescribed (if any)	Codeine/ Morphine/ Fentanyl/ Tramadol/ Oxycodone/ Other (please specify)/ no opioids prescribed
Date opioid analgesia first administered	Date (dd/mm/yyyy)
Time opioid medication is administered to patient	24 hour clock
Route	PO/ IV
(If regular) daily dose	mg
(If PRN) total dose in first 72 hours	mg

(If yes) Date opioids first administered	Date (dd/mm/yyyy)
(If yes) Time opioid medication first administered as per drug chart?	24 hour clock
Further analgesic modalities	PCA/ ketamine/ local nerve blocks/ other (please specify)
Transfer to different hospital	
Patients with predicted severe disease discussed with specialised pancreas service ( Appendix B ) in first 72 hours from admission	Yes/ No/ not applicable
Patient transferred to a different hospital in the first 72 hours?	Yes/No
(If yes) Date of transfer	Yes/No
(If yes) Location transferred to	List of hospitals
(If yes) Reason for transfer to different hospital?	Severe disease/ requires ERCP/ requires interventional management of local complication/ other (free text)
ERCP	
Cholangitis in first 72 hours ( Appendix F )	Yes/ No
Cholestasis in first 72 hours (radiological + deranged LFTs)	Yes/ No
ERCP performed in the first 72 hours	Yes/ No
Fluid management*	
Baseline variables	
Bag 1	
Date of administration	Date (dd/mm/yyyy)
Time of administration	Time (24-hour)
Volume administered	Volume (ml)
How long does fluid run for?	Time (hours)
Type of fluid	0.9% Normal saline/ Hartmann's/ plasmalyte/ colloid/ 0.45 saline + dextrose/ 0.18 saline + dextrose/ other (please specify)
Further administration of intravenous fluid (IVF) in the first 3 days of admission? ( Appendix B )	Yes/no
Bag 2	
Date of administration	Date (dd/mm/yyyy)
Time of administration	Time (24-hour)

Volume administered	Volume (ml)
Time fluid is administered	Time (hours)
Type of fluid	0.9% Normal saline/ Hartmann's/ plasmalyte/ colloid/ other (please specify)
Further administration of intravenous fluid (IVF) in the first 2 days of admission?	Yes/no
Documented fluid review after 12 hours ( $\pm$ 4 hours)	Yes/no
Documented fluid review after 24 hours ( $\pm$ 4 hours)	Yes/no
Documented fluid review after 48 hours ( $\pm$ 4 hours)	Yes/no
Documented fluid review after 72 hours ( $\pm$ 4 hours)	Yes/no
Early Nutritional support	
On admission patient kept nil by mouth (NBM)	Yes/no

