**Appendix B - Definitions**

Local complication	Definition
Acute pancreatitis (AP)	
The diagnosis of acute pancreatitis requires two of the following three features:
 
 
● Abdominal pain consistent with acute pancreatitis (acute onset of a persistent, severe, epigastric pain often radiating to the back)
 
● Serum lipase activity (or amylase activity) at least three times greater than the upper limit of normal
 
● Characteristic findings of acute pancreatitis on contrast-enhanced computed tomography (CECT) and less commonly magnetic resonance imaging (MRI) or transabdominal ultrasonography (24).
 

Chronic pancreatitis (CP)	
Identification of the following signs via high quality imaging modalities (computed tomography, magnetic resonance imaging):
 
 
● Increased density of the parenchyma
 
● Atrophy of the gland
 
● Calcification
 
● Pseudocysts and irregularities of the main pancreatic duct and its side branches.
 
 
Diagnosis should be based on imaging performed in symptomatic patients presenting with indicators suggestive of pancreatic disease (25).

Specialised pancreas service	Performs elective pancreatic resections
Gallstone (biliary) AP	Confirmation of gallstones using radiological imaging (including abdominal or endoscopic ultrasonography, CT and magnetic resonance cholangiopancreatography)(14,16)
Alcohol induced AP	
History of alcohol consumption (>10g) prior to the diagnosis of acute pancreatitis.
 
10g alcohol is approximately:
 
 
● 300ml beer
 
● 100ml wine
 
● 30ml spirits
 
 
(14,16)

Hypertriglyceridaemia induced AP	
 
● Biliary and alcohol-induced pancreatitis ruled out
 
● Serum triglyceride >1,000 mg/dl ((14).
 

Necrotising AP	
Inflammation associated with pancreatic parenchymal necrosis and/or peripancreatic necrosis, CECT criteria:
 
 
● Lack of pancreatic parenchymal enhancement by intravenous contrast agent and/or
 
● Presence of findings of peripancreatic necrosis (see below—ANC and WON)(24)
 

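### Appendix F leaves the cholangitis field behind the ERCP indicator open enough that biliary pancreatitis with cholestasis can be coded as cholangitis

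*Protocol*

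**What the plan says.** Protocol section 3, Table 1, row 12 sets the indicator: "ERCP is indicated in patients with biliary pancreatitis and acute cholangitis within 48 hours of admission". Its metrics column asks whether ERCP was done, when (in hours), and "Indication: cholangitis or cholestasis".

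The ERCP block of section 5.5 has three Yes/No items and nothing else:
- "Cholangitis in first 72 hours", with a reference to Appendix F;
- "Cholestasis in first 72 hours (radiological + deranged LFTs");
- "ERCP performed in the first 72 hours".

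Appendix F has three classes with two numbered items each:
- A, systemic inflammation: fever above 38 degrees; white cells below 4 or above 10 and/or CRP of at least 1, with no unit.
- B, cholestasis: bilirubin of at least 2 mg/dL; liver tests above 1.5 times the standard.
- C, imaging: biliary dilation; "Evidence of aetiology on imaging".

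It does not say how items combine within a class, or which classes are needed.

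Two other places bear on the reading. Appendix B defines gallstone pancreatitis by "Confirmation of gallstones using radiological imaging". Section 1 states that "AP is characterised by a local and systemic inflammatory response".

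**The concern.** The cholangitis item is the only one in section 5.5 that separates the patients indicator 12 is about from other biliary patients. Within biliary pancreatitis, two of the three classes may discriminate little: class C through the gallstones and class A through the inflammation of pancreatitis. The label would then rest mainly on class B, and cholangitis would largely merge with cholestasis, which the form treats as a separate item.

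Patients without cholangitis could then enter the denominator. Indicator 12 counts toward the primary outcome (overall compliance, section 4.1) and is one of the domains compared between hospitals (section 4.2, and the funnel plots in section 8). Up to eight collectors per hospital, who may include medical students and junior doctors, would apply the criteria. Different local readings could therefore appear as differences in hospital performance.

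**Working it through.** **Step 1. Reading the text under the strictest rule (one item from each of A, B and C).** Take a biliary patient with no cholangitis whose cholestasis item is Yes.

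| Class | What can satisfy it | Source |
|---|---|---|
| C | gallstones already seen on imaging | Appendix F second imaging item, with Appendix B |
| B | deranged liver tests, if above 1.5 times the standard | Appendix F, with the cholestasis item in 5.5 |
| A | white cells above 10, or CRP of at least 1, supplied by the pancreatitis | Appendix F, with section 1 |

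All three classes are met, so the patient is coded as cholangitis. Looser rules code more patients.

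**Step 2. The CRP unit.** Appendix F uses mg/dL for bilirubin but gives no unit for CRP. Since 1 mg/dL is 10 mg/L, two collectors could apply cut-offs ten times apart.

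**Step 3. Can it be repaired from the data?** Section 5.5 has no field for temperature, white cells, bilirubin, liver test values or biliary dilation. CRP appears only as a severity-prediction method. The nearest record of a clinician's diagnosis is the cholangitis option under antibiotic indication, available only in patients given antibiotics. Reclassification would mean returning to the notes through the local re-identification key (section 5.3).

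**Step 4. Direction and size.** The protocol states no cholangitis rate, ERCP rate or expected adherence, so there is no planned figure to reproduce. Every input below is an assumption.

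- c: true cholangitis share of biliary pancreatitis, 5–15%.
- P(A): 0.70–0.95, and P(B): 0.30–0.80, in biliary patients without cholangitis. P(C) = 1, the literal reading.
- aT: ERCP rate in true cases, 60–90%. aF: ERCP rate in false positives, 5–30%.
- True cases are always flagged.

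Formulas, with f the share of non-cholangitis patients meeting the rule:
- flagged = c + (1 − c)f
- PPV = c / flagged
- observed adherence = PPV·aT + (1 − PPV)·aF
- gap = aT − observed = (1 − PPV)(aT − aF)

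f is P(A)·P(B) if all three classes are needed, P(A) if A plus either B or C is needed, and 1 if any class suffices.

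| Rule | Flagged | PPV | Gap (points) |
|---|---|---|---|
| A and B and C | 25–80% | 6–46% | 16.3–79.5 |
| A and (B or C) | 72–96% | 5–20% | 24.0–80.5 |
| any one class | 100% | 5–15% | 25.5–80.7 |

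Middle case, all three classes needed (c = 0.10, P(A) = 0.9, P(B) = 0.5, aT = 0.80, aF = 0.15):
- flagged = 0.10 + 0.90 × 0.45 = 0.505
- PPV = 0.10 / 0.505 = 0.198
- observed = 0.198 × 0.80 + 0.802 × 0.15 = 0.279, against a true 0.80.

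With aF = 0.40 instead, observed = 0.198 × 0.80 + 0.802 × 0.40 = 0.479. If aF equals aT, the gap is zero.

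**Step 5. Effect of limiting the second imaging item to a bile-duct cause.** Keep the middle case, but let class C be met in 10–30% of patients without cholangitis (assumed). At 10%, flagged = 0.10 + 0.90 × 0.045 = 0.1405 and PPV = 0.712. At 30%, flagged = 0.10 + 0.90 × 0.135 = 0.2215 and PPV = 0.451. Observed adherence is 44–61% with aF = 0.15 and 58–68% with aF = 0.40. The bias shrinks but does not vanish.

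**Step 6. The numerator.** Indicator 12 sets 48 hours and its metric asks for hours. Section 5.5 records only ERCP within 72 hours, without a time. An ERCP between 48 and 72 hours cannot be told from an earlier one and may count as compliant, which pushes adherence upward.

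**The case against.** The best reply concerns the imaging item. It sits in a table of criteria for cholangitis, so a collector may take the aetiology to be that of the cholangitis, not of the pancreatitis. No passage links it to the Appendix B definition. That reading is fair, and Step 5 shows that under it the false positives fall sharply. But nothing in Appendix F limits the item to a bile-duct cause, and the two readings give very different denominators. The appendix also names a published standard that may contain a combination rule. That cannot be checked here, and collectors work from what is printed.

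Second, no section says how indicator 12 is scored, and an analysis plan that is not shown may do so. This stands as to scoring. It does not help with classification, because an analysis plan cannot use component items that were never collected. Nor do the documents settle whether the metric's mention of cholestasis is meant to widen the indicator. If it is, the merging matters less, and row 12 should say so.

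Third, the separate cholestasis item needs a radiological component as well as deranged liver tests, so it is not the same as class B. That is right. The two fields overlap heavily but are not identical.

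Three further inferences are tempting and not supported:
- Comparing CRP of at least 1 with the severity cut-off of 150 as a 150-fold conflict. Neither has a unit, and they serve different purposes.
- Expecting hospitals with more gallstone disease to look worse. In this domain adherence is a proportion within biliary patients, so their number cancels.
- Saying that clinicians who do not perform ERCP in cholestasis are right and scored wrong. The documents do not decide that, and this review does not either.

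**Conclusion.** The coding defect holds on the text alone: no combination rule, no CRP unit, and an imaging item that the defining gallstones can satisfy. The indicator 12 denominator can include patients without cholangitis, and the listed data cannot sort them out afterwards.

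The bias from this source is downward if falsely coded patients have ERCP less often than true cases, as every scenario in Step 4 assumes. Its size cannot be estimated from the protocol. The 72-hour numerator may offset part of it.

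A reader might infer that most biliary pancreatitis would be coded as cholangitis and adherence badly understated. The documents do not show either. Under the three-class rule, flagging more than half of the patients without cholangitis needs P(A)·P(B) above 0.5, for example P(B) above 0.5/0.9 = 0.56 when P(A) is 0.9, and the protocol gives neither share. The gaps in Step 4 rest wholly on assumed rates, and raising one of them (aF from 15% to 40%) moves the middle case from 28% to 48%. Indicator 12 is also one of twelve domains, so any effect on overall compliance depends on how the domains are combined.

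This should be corrected, because the repair is cheap if made before data collection and costly afterwards.

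**What to change.** In Appendix F:
- state how many items are needed within a class and which classes are required;
- give the CRP unit;
- state, for coding purposes, that the second imaging item means imaging evidence of a bile-duct cause, not the gallstones that already define biliary pancreatitis.

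In section 5.5, record which A, B and C items were met, and whether the treating team documented acute cholangitis. Report indicator 12 under the criteria and, as a sensitivity analysis, under the documented diagnosis. Show cholestasis without cholangitis separately.

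Reconcile the 48-hour window in Table 1 with the 72-hour ERCP item, and record the time of ERCP, which the Table 1 metric already asks for.

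The cost is some appendix wording and a few form fields, with no extra patients or tests. The sensitivity analysis will depend on the quality of the notes, which is why the documented diagnosis is added beside the criteria and does not replace them.
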